5.7.2.6. Adverse Events of Special Interest

The AESI for this study is TEs, which are adjudicated by EAC blinded to treatment. The number and percentage of participants with adjudicated TEs and the number of TEs in each treatment group and total will be summarized by SOC and PT.

Among participants with TEs, the number and percentage of participants in each treatment group will be summarized for the following categories:

- Did not use anticoagulants
- Used anticoagulants before the first TE
- Used anticoagulants after the first TE

5.7.3. Laboratory Tests

Testing related to clinical laboratory is defined in Protocol Section 9.2.2.

The following assays will be performed at the local laboratory:

- Hematology: Hemoglobin, hematocrit, white blood cell (WBC) count, platelet count, and WBC differential
- Coagulation: International normalized ratio
- Serum chemistry (if available per clinical routine): Sodium, potassium, chloride, carbon dioxide (bicarbonate), glucose, blood urea nitrogen, creatinine, aspartate aminotransferase, alanine aminotransferase, albumin, alkaline phosphatase, calcium phosphorus, and total, direct, and indirect bilirubin
- Serum or urine pregnancy test (in female participants of childbearing potential)
- Anti-fXa activity (for participants treated with an oral FXa inhibitor > 15 hours prior to randomization or unknown time of the last dose)

The following assays will be performed at a central laboratory:

- Anti-fXa activity (Note: The evaluation of the secondary efficacy endpoint will use only central, and not local, anti-fXa activity)
- Antibodies to FX, FXa, and and exanet
- Neutralizing antibodies to fX, FXa and and exanet (modified Bethesda assay [BU/mL])
- Thrombin generation
- TFPI

Analyses of clinical chemistry, hematology, and coagulation parameters will be performed by treatment.

Descriptive statistics will be performed for the values at each visit, as well as change from baseline to each visit. Tabulations will be performed for abnormal values relative to normal ranges at each visit, as well as shifts from baseline to each visit.

Clinically significant laboratory test abnormalities apply to the following analytes:

- Hematology: Hemoglobin, hematocrit, WBC count, platelet count, and WBC differential
- Serum chemistry (if available per clinical routine): Sodium, potassium, chloride, carbon dioxide (bicarbonate), glucose, blood urea nitrogen, creatinine, aspartate aminotransferase, alanine aminotransferase, albumin, alkaline phosphatase, calcium phosphorus, and total, direct, and indirect bilirubin

Section 6.1 details the clinically significant criteria to be followed.

5.7.4. Vital Signs

Vital signs, including temperature, systolic blood pressure, diastolic blood pressure, heart rate, and respiratory rate, will be summarized using actual values and change from baseline at prespecified time points for each treatment group and total. In addition, the number of participants having clinically significant vital signs at each visit will be tabulated. Section 6.1 details the clinically significant criteria to be followed.

A by-participant listing of vital sign results will be provided.

5.7.5. Hospitalizations

Hospitalization endpoints include the following:

- Length of the initial hospitalization for a primary bleeding event. The first duration (in hours) is from the initial hospitalization to randomization, and the second duration (in days) is from randomization to the first discharge date. The total duration from the initial hospitalization to the first discharge date will also be summarized.
- Total time (in days) admitted to the intensive care unit (ICU) during the initial hospitalization.
- Rate of rehospitalization, including the total number of rehospitalizations and the total number of days rehospitalized, at 30 days post-randomization.

The length of the initial (index) hospitalization, the total time spent in the ICU, and the occurrence of rehospitalizations (including the total number of rehospitalizations and the total number of days rehospitalized) up to 30 days post-randomization will be summarized descriptively by treatment group and total.

If the time between consecutive hospitalizations is < 6 hours apart and the discharge location for the first event is either an ICU or an "inpatient non-ICU" environment, then these events are considered to be a single hospitalization. If, however, the discharge location of the first event is home care, home hospice, long-term care hospital, intermediate care facility, outside hospital, or

other, then the subsequent event is to be considered a rehospitalization regardless of the time between the events.

By-participant listings of the initial hospitalization and rehospitalizations will be provided.

5.7.6. Invasive Intracranial Procedures

Invasive intracranial procedures performed post-randomization to manage the intracranial hematoma and/or its complications are found in Protocol Appendix G.

Number of procedures, and the number and proportion of participants with at least 1 of invasive intracranial procedures performed post-randomization will be summarized descriptively by treatment group and total. All surgeries and interventional procedures specifically intended to manage the hematoma and/or its complications will be tabulated.

5.7.7. Immunogenicity

Tabulations of immunogenicity results up to Day 30 (antibodies to FX, FXa, and andexanet, and neutralizing antibodies to FX, FXa, and andexanet) will be provided. A positive antibody response will be defined as a positive titer that occurs after baseline or an increase in titer from baseline to post-baseline. Baseline values are considered data captured within 120 minutes prior to randomization. Rates of antibody response to various antigens (andexanet, FX, and FXa) will be summarized by the dose of andexanet (high versus low) for the andexanet subset of Safety Set.

5.8. Subgroup Analyses

The following subgroup analyses will be performed for the primary endpoint on the ITT Set using the same stratified CMH test described in Section 5.3.1. For subgroups with < 5 participants, only summary statistics will be presented; a statistical inferential analysis will not be performed.

- Age (< 65 years, 65 to 74 years, or \geq 75 years)
- Sex (male or female)
- Race (groups as collected on electronic case report form (CRF))
- Geographic region (North America, Europe, or Asia)
- Prior FXa inhibitor (apixaban, edoxaban, or rivaroxaban)
- Indication for prior FXa inhibitor (atrial fibrillation/flutter, venous thromboembolism including prevention and treatment, or other)
- Baseline anti-fXa activity (< $30 \text{ or} \ge 30 \text{ ng/mL}$)
- Baseline anti-fXa activity (< 75 or \ge 75 ng/mL)
- Determination of the ICH score at baseline (< 3 or \geq 3)
- Baseline volume of hematoma ($< 30 \text{ or} \ge 30 \text{ mL}$)
- Baseline volume of hematoma (< 0.5 or \ge 0.5 mL)

- Index bleeding location (ICrH-intracerebral hemorrhage, ICrH-intraventricular hemorrhage, intracranial-multicompartment, intracranial-subdural, and intracranial-subarachnoid)
- Time to randomization since the last FXa inhibitor dose (< 8 or \geq 8 hours)
- And examet dose (high dose versus UC and low dose versus UC)
- UC received (and examet vs PCC, and examet vs non-PCC)

Forest plots of the treatment differences in the proportion of participants achieving effective hemostasis will be generated for the subgroup analyses on the ITT Set.

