10.1. General Considerations

During the conduct of the study, the Sponsor and Investigators will be blinded to the aggregated efficacy and safety summaries. Also, all unblinded analyses that are required to support the DSMB will be performed by an independent unblinded statistician. These analyses will be performed under the direction of the DSMB according to the Statistical Analysis Plan (SAP) and the DSMB Charter. The results of these unblinded analyses will not be available to the Sponsor or Investigators until after database lock, unless the DSMB recommends early termination of the trial.

The safety interim analyses will follow the same procedures as the efficacy interim analysis (see Section 10.7), with the Sponsor remaining blinded to the results of these analyses unless the DSMB recommends stopping the trial early.

Once the study is complete and the final database lock is performed, the study will be fully unblinded and final analyses will be performed.

All efficacy hypothesis tests will be 2-sided and performed at the 0.05 significance level. Adjustments for the overall type I error for the planned interim efficacy analysis are described in Section 10.7.

It is anticipated that statistical summaries will be performed using SAS Version 9.2 (SAS Institute, Inc., Cary, NC, USA) or higher. Additional software may be used for the production of graphics and for statistical methodology not available in SAS.

All efficacy and safety endpoint parameters will be summarized descriptively.

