10.8. Subgroup Analyses

Subgroup analyses may include, but not necessary be limited to, the following parameters: baseline anti-fXa activity above and below 30 ng/mL, baseline anti-fXa activity above and below 75 ng/mL, age (less than 65, 65-74, 75 or greater), sex, race (all groups with 5 or more patients), geographical region (North America, Europe, Asia), FXa inhibitor at randomization, indication for FXa inhibitor (atrial fibrillation, VTE, other), time at randomization since last FXa inhibitor dose (within 8 hours or more than 8 hours), andexanet dose, hematoma expansion risk as measured by baseline hematoma volume (< 30 mL, \geq 30 mL; < 0.5 mL, \geq 0.5 mL), determination of ICrH score at baseline(< 3, \geq 3), baseline intracranial bleed location, and usual care received (andexanet vs PCC, andexanet vs non-PCC).

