5.3.2. Main Analytical Approach

Primary analysis will be performed using a CMH test stratified by time from symptom onset to the baseline imaging scan (< 180 minutes versus \geq 180 minutes). The difference in the proportion of participants with effective hemostasis, its 95% CI, and the p-value will be estimated.

A by-participant listing of effective hemostasis will be provided.

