6.2.2.1. Demographics and Disease Characteristics (Bleeding)

The following demographic and baseline disease characteristics variables will be summarized by treatment group and total using descriptive statistics. No inferential analyses of these data are planned.

• Sex (male or female).

- Race (American Indian or Alaska native, Asian, Black or African American, Native Hawaiian or other pacific islander, White, or other).
- Ethnicity (Hispanic or Latino, not Hispanic Or Latino, not reported, or unknown).
- Age (< 65 years, 65 to 74 years, or \geq 75 years).
- Height (cm).
- Weight (kg).
- Body mass index (< 25 kg/m², 25 to < 30 kg/m², or \ge 30 kg/m²).
- Tobacco use (current, former, or never).
- Geographic region (North America, Europe, or Asia).
- FXa inhibitor (apixaban, edoxaban, or rivaroxaban).
- Indication of FXa inhibitor (atrial fibrillation, venous thromboembolism, or other).
- Intended UC agent: PCC, other
- Time since the last FXa inhibitor dose to scan for bleeding (< 180 minutes versus \geq 180 minutes).
- Baseline anti-fXa activity (< 30 to \ge 30 ng/mL and < 75 to \ge 75 ng/mL).
- Participant presentation location (emergency room/department, ICU, inpatient ward, stroke clinic, transfer from outside hospital, or other).
- Approximate hematoma volume of baseline CT/MRI (< 30 and \ge 30 mL; < 0.5 and \ge 0.5 mL).
- Mechanism of injury (spontaneous ICrH and trauma ICrH); participants who will not have bleeding as a result of trauma will be considered as spontaneous bleeding.
- Time from hospitalization to study treatment.
- Time from the last FXa inhibitor dose to treatment (< 8 or \ge 8 hours).
- Time from symptom onset to baseline CT or MRI scan (< 180 minutes versus ≥ 180 minutes).
- Time from CT or MRI scan to treatment.
- Time from bleeding to treatment onset.
- Primary bleeding location per adjudication (intracerebral hemorrhage, not intracerebral hemorrhage, and multicompartment, where intracerebral hemorrhage includes intracerebral or intraventricular bleeding, and not intracerebral hemorrhage includes subdural or subarachnoid bleeding).
- Intracerebral hemorrhage (ICH) score (< 3 or \geq 3).

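### SAP 5.8 tests the primary endpoint separately inside up to about 37 subgroup levels, with no treatment-by-subgroup interaction test and no exploratory label

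*SAP*

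**What the plan says.** SAP 5.8 sets the method: "The following subgroup analyses will be performed for the primary endpoint on the ITT Set using the same stratified CMH test". It lists 15 items. Thirteen are baseline factors. The other two, andexanet dose and usual care received, set part of one arm against the other arm and are outside this point.

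The only limit on inference is a size rule: "For subgroups with < 5 participants, only summary statistics will be presented; a statistical inferential analysis will not be performed". Section 5.8 also asks for forest plots of the treatment differences. It refers to SAP 5.3.1 for the test. The full output of that analysis is given in SAP 5.3.2: "The difference in the proportion of participants with effective hemostasis, its 95% CI, and the p-value will be estimated".

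On the significance level, Protocol 10.1 says: "All efficacy hypothesis tests will be 2-sided and performed at the 0.05 significance level". SAP 5.8 names no other level. The hierarchical procedure in SAP 5.1.1 and Protocol 10.5.4.1 covers the primary and secondary endpoints only. Protocol 10.8 gives an open list ("Subgroup analyses may include, but not necessary be limited to, the following parameters") and no method.

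Neither subgroup section contains an interaction or heterogeneity test, a multiplicity statement, or a label such as exploratory or descriptive. The interaction terms elsewhere in the plan are treatment by time or visit, in the repeated-measures models and the anti-fXa imputation model.

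**The concern.** A subgroup analysis asks whether the treatment effect differs between levels of a factor. A p-value within one level asks whether there is an effect in that level, and the answer depends heavily on how many participants the level holds. When the effect is the same everywhere, a larger level will often be significant and a smaller one not. That pattern is easily read as effect modification.

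As written, the plan produces many such within-level results and no test of the question they will be used to answer. This matters most if the trial stops at the interim. SAP 1.2 and 5.9.1 then make the dataset of about 450 the confirmatory one for efficacy and the basis for regulatory submission, and within-level power is lowest there.

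**Working it through.** **Inputs from the documents.** Rates of 70% and 80%, 450 per group, about 90% power (SAP 3); interim at about 450 participants in total (SAP 1.2); nominal levels 0.0310 and 0.0277 (SAP 2); 0.05 for other efficacy tests (Protocol 10.1). The documents give no subgroup prevalences.

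**1. The plan's own power figure.** Pocock-type spending at half information is 0.05 × ln(1 + (e − 1) × 0.5) = 0.0310, which leaves 0.0277 at the final analysis. With 450 per arm, power at 0.0277 alone is 0.898, and over both looks it is 0.909. Assumed losses of 5% and 10% give 0.895 and 0.877. The stated 90% is reproduced.

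**2. Number of levels.** Age 3, sex 2, race 6, region 3, inhibitor 3, indication 3, anti-fXa at 30 ng/mL 2, anti-fXa at 75 ng/mL 2, ICH score 2, volume at 30 mL 2, volume at 0.5 mL 2, bleed location 5, time since dose 2. The sum is 37. SAP 5.8 does not count the race groups ("Race (groups as collected on electronic case report form (CRF"); six are listed in SAP 6.2.2.1 ("Race (American Indian or Alaska native, Asian, Black or African American, Native Hawaiian or other pacific islander, White, or other"). This is a ceiling:
- The two anti-fXa items cut the same variable, and so do the two volume items.
- Volume below 0.5 mL is outside Inclusion Criterion 3, so that level should be nearly empty.
- Subdural and subarachnoid levels depend mainly on participants enrolled before Amendment 1.

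**3. Discordance under a uniform effect, even two-level split.** With n per arm in a level, power = Φ{[0.10 − 1.96 × √(0.375/n)] / √(0.37/n)}. Here 0.375 = 2 × 0.75 × 0.25 and 0.37 = 0.7 × 0.3 + 0.8 × 0.2.
- N=900, n=225: (0.10 − 1.96 × 0.0408)/0.0406 = 0.49, so power is 0.689. P(one level significant, the other not) = 2 × 0.689 × 0.311 = 0.43.
- N=450, n=112: (0.10 − 1.96 × 0.0579)/0.0575 = −0.23, so power is 0.408. P(discordant) = 2 × 0.408 × 0.592 = 0.48.

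The only assumption beyond the plan's own rates is the even split. An interaction test on the same factor would wrongly reject in about 5% of trials.

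**4. No effect, whole family.** For 37 independent tests, 1 − 0.95^37 = 0.85, with 37 × 0.05 = 1.85 false positives expected. The levels overlap, so this is too high. Simulating the 13 factors with 75% response in both arms and N=900 gave 0.66 to 0.68. A second simulation that added the dose and usual-care contrasts, with two assumed sets of prevalences and N of 450 or 900, gave 0.66 to 0.69. All simulations treated separate factors as independent.

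**5. The alternative on the same family basis.** Thirteen interaction tests at 0.05 give 1 − 0.95^13 = 0.49 if independent, and 0.48 to 0.54 in simulation. The like-for-like comparison is roughly two thirds against about one half.

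**6. Power of an interaction test.** Take effects of 15 and 5 points, an even split, and the planning rates for the variance. The SE of the contrast is √(2 × 0.37/n).
- N=900: SE = √(0.74/225) = 0.057; Φ(0.10/0.0573 − 1.96) = Φ(−0.22) = 0.41.
- N=450: SE = √(0.74/112) = 0.081; Φ(0.10/0.0813 − 1.96) = Φ(−0.73) = 0.23.

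**The case against.** **P-values may not be planned.** SAP 5.8 never mentions them. It points to 5.3.1, whose summary is a difference with a 95% CI, and names only forest plots as output. SAP 5.1 presents inferential statistics only where specified, and a separate Data Presentation Plan governs tables and figures. This reading is possible but weak. Section 5.8 names a test and withholds inference only below 5 participants, and sensitivity analysis 4 in SAP 5.3.3 cites the same 5.3.1 for a comparison it judges at p < 0.05.

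**Error control is intact.** A reader might infer that the subgroup tests inflate the trial's type I error. The documents do not support that. Success is defined on the overall comparison alone, the hierarchy names only the primary and secondary endpoints, and nothing allows a subgroup to establish efficacy. This stands in full. It does not tell a reader how to interpret the subgroup results.

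**Interaction tests also give false positives.** This stands. Setting the two-thirds family figure beside a 5% rate per interaction test, or calling it 13 times the allowed error, would compare unlike quantities. The plan claims no family-wise level for subgroups.

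**Confidence intervals carry the same pattern.** This also stands. An interval that excludes zero in one level and includes it in another looks just as discordant, so removing p-values is not enough without an interpretation rule.

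**The simulated figures rest on assumed prevalences.** True of the two-thirds figure, and of any higher discordance rate for uneven or many-level factors. The 43% and 48% need only the even split.

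**Conclusion.** The point holds as a gap in interpretation and is cheap to close. SAP 5.8 plans within-level tests for up to about 37 levels of 13 baseline factors. Neither document plans a test of whether the effect varies, or says that the subgroup results are exploratory.

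The firmest measure is the 43% (N=900) or 48% (N=450) chance that an evenly split factor looks discordant when the effect is uniform. The advantage under no effect is modest on a family basis and rests on assumed prevalences and independent factors.

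Two stronger readings are not supported. The trial's confirmatory conclusions are not at risk. Nor would interaction tests settle whether the effect varies: at 41% and 23% power for a 15 versus 5 point contrast, they would usually miss it.

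**What to change.** In SAP 5.8:
- Report the difference in proportions and its 95% CI for each level, without within-level p-values.
- Add one treatment-by-subgroup interaction (heterogeneity) test per baseline factor, adjusted for the onset-to-scan stratum. Name the scale in advance; the risk difference matches the forest plot. Exclude the andexanet dose and usual care received contrasts, which do not allow an ordinary interaction test as defined.
- State that subgroup results are exploratory and unadjusted for multiplicity.
- State that no claim of a differing effect will rest on within-level significance, or on whether a level's CI excludes zero.
- State that interaction tests have low power here and that a non-significant result is not evidence of a uniform effect.

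The cost is SAP wording and one model per factor on data already collected. The primary and secondary analyses, sample size and stopping rule do not change. Within-level p-values can no longer be quoted as evidence.

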1. INTRODUCTION

This statistical analysis plan (SAP) describes the statistical methods and outputs for analyzing data for Protocol 18-513, titled "A Randomized Clinical Trial of Andexanet Alfa in Acute Intracranial Hemorrhage in Patients Receiving an Oral Factor Xa Inhibitor." Standard data presentation instructions and table, figure, and listing specifications are contained in the Data Presentation Plan in a separate document.

All events and analyses occurring by Day 30 will be described in a primary clinical study report. Additional events and analyses for the period between Day 30 and Day 120 (if applicable) will be described in a safety follow-up clinical study report. All analyses and outputs described in this document are for the primary clinical study report.

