5.3.1. Estimand

Table 3 below describes the attributes of the Primary (Composite) estimand.

Page 17 of 52 Alexion Confidential

Estimand	Attributes of Estimand				
	Treatment	Endpoint	Population	Intercurrent Events Handling	Statistical Summary
Primary (composite estimand)	Andexanet vs usual care	Proportion of participants with effective hemostasis	ITT Set	Rescue medications/procedures: All participants will be considered as poor/none (not effective) for effective hemostasis if meeting Criteria 1 and/or 2 below: 1. Initiation of rescue therapies (medication or procedures) starting ≥ 3 hours post- randomization and up to < 12 hours post-	Difference in the proportion of participants with effective hemostasis between the 2 treatment groups, and its 95% confidence interval as estimated by a CMH test stratified by the time from symptom onset to baseline imaging assessment (< 180 minutes vs ≥ 180 minutes)

Table 3:Attributes of Primary (Composite) Estimand

Estimand	Attributes o	of Estimand			
	Treatment	Endpoint	Population	Intercurrent Events Handling	Statistical Summary
				change from baseline to 12 hours in hematoma volume.	
				 Core imaging laboratory request for EAC review. 	
				4. Misadministration of procoagulant blood products contrary to treatment allocation within 3 hours pos-randomization (including andexanet in usual care arm)	
				5. Performance of a surgery or interventional procedure to treat the index hematoma or that could impact hematoma volume within 3 hours post- randomization	
				Nonevaluable events : There are 2 types of reasons for nonevaluable hemostatic status:	
				 Cases deemed nonevaluable due to administrative reasons (for example, but not limited to, follow-up scan not available, not performed not 	
				performed, not interpretable, or transfer of the participant to another facility for administrative purposes)	
				 Cases deemed nonevaluable due to clinical reasons (for example, but not 	

Table 3:Attributes of Primary (Composite) Estimand

Estimand	Attributes of Estimand					
	Treatment	Endpoint	Population	Intercurrent Events Handling	Statistical Summary	
				limited to, the participant died due to index bleed or the participant had unplanned surgery draining hematoma) The decision of the EAC is considered final. The nonevaluable status due to both reasons will be treated as poor/none in the primary analysis.		

 Table 3:
 Attributes of Primary (Composite) Estimand

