5.5.6. Rescue Therapy

Rescue therapies include rescue medications and rescue procedures including surgeries. The number of participants receiving rescue therapies (medication or procedures) between 3 and 12 hours post-randomization, as well as the total number of therapies received, will be summarized based on dose of andexanet received (low, high, and total) or the type of UC initially received (PCC, other, no treatment, and total). The CMH test stratified by time from symptom onset to the baseline imaging scan will be used to test the treatment difference in the proportion of participants receiving at least 1 rescue therapy between andexanet and UC. The p-value and 95% CI of the difference in proportion will be presented.

The types of rescue medications used will be tabulated by treatment group; participants reporting > 1 medication within an Anatomical Therapeutic Chemical (ATC) classification or a generic name will be counted only once for that class or name. In addition, the surgeries/procedures used to treat the index hematoma or could impact hematoma volume will be tabulated by treatment group; participants reporting > 1 surgery/procedure will be counted only once for that surgery/procedure.

A by-participant listing of rescue therapies will be provided.

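### SAP 5.8 gives the UC-received rows, and less seriously the andexanet-dose rows, the same CMH inference and forest plot as randomized subgroups, although they are not randomized comparisons

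*SAP*

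**What the plan says.** SAP 5.8 analyses the primary endpoint in each listed subgroup "using the same stratified CMH test described in Section 5.3.1", and adds "Forest plots of the treatment differences in the proportion of participants achieving effective hemostasis". Its only restriction is that subgroups of fewer than five participants get summary statistics alone. Most rows divide both arms by a baseline feature. Two do not:

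- "UC received (and examet vs PCC, and examet vs non-PCC") divides only the usual-care arm.
- "And examet dose (high dose versus UC and low dose versus UC") divides only the andexanet arm.

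The summary measure in the section that 5.8 refers to is "Difference in the proportion of participants with effective hemostasis between the 2 treatment groups, and its 95% confidence interval", with onset-to-scan time (under or over 180 minutes) as the sole stratifier. Protocol 10.8 lists the same usual-care contrast, also without comment.

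Protocol 3.1 leaves usual care to the treating team, to be started in the three hours after randomization, in an open-label trial. Protocol 3.2.1 also has the investigator record, before randomization and for every patient, which type of agent would be used if the patient were allocated to usual care. Randomization has been stratified on that answer since Amendment 1. It is in neither subgroup list.

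**The concern.** A subgroup difference has the protection of randomization only if both arms are divided by something fixed before allocation. Agent received has no counterpart in the andexanet arm, so the UC-received rows compare everyone on one side with a selected part of the other. Protocol 3.2.1 itself raises the possibility that recipients of factor concentrates differ in demographics or in severity at baseline. It gives this, alongside regional variation in use, as the reason for the stratum. The 5.8 test does not adjust for intended agent.

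At stake is the reading of supportive results. Because the two biases have opposite signs, the pair can look like an andexanet effect that depends on the comparator, displayed beside rows that are genuine randomized comparisons.

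The dose rows share the structure, since part of the andexanet arm is compared with an undivided usual-care arm. But under Protocol 6.2 the regimen depends mainly on facts fixed before randomization: the inhibitor, and the amount and timing of its last dose.

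**Working it through.** **Inputs.** From the documents: 70% effective hemostasis on usual care and 450 per group (SAP 3), or 225 per group if the trial stops at the interim with N = 450 (SAP 1.2). Assumed, because the documents give no figure: PCC share *s* = 50–85%, and a prognosis gap *g* = 5–15 points between non-PCC-type and PCC-type patients. The plan states no figure for these rows, so there is none to reproduce. Its general figure of about 90% power does check (two-look power 91.2% with no loss, 89.7% with an assumed 5% loss) but has no bearing here.

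**1. Bias with no true effect.** Hold both arms at 0.70 overall and let PCC-type patients do worse. The success rates are then

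- PCC type: 0.70 − (1 − s)g
- non-PCC type: 0.70 + s·g

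The expected differences, andexanet minus comparator, are +(1 − s)g versus PCC and −s·g versus non-PCC. Weighted by share they cancel: s(1 − s)g − (1 − s)s·g = 0. So the whole-arm comparison is untouched, and opposite signs are forced whenever g is not zero. If PCC-type patients do better, both signs reverse.

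**2. How often a row looks significant.** For a large-sample two-proportion test at nominal two-sided 0.05, without the onset-time stratum, the chance of significance in the direction of the bias is Φ((d − 1.96·SE₀)/SE₁), with SE₀ pooled and SE₁ unpooled. Worked case, s = 0.50, g = 0.10, 450 per arm, versus PCC:

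- d = 0.70 − 0.65 = 0.05, with 450 against 225 patients
- pooled rate (315 + 146.25)/675 = 0.683, so SE₀ = 0.0380
- SE₁ = √(0.21/450 + 0.2275/225) = 0.0384
- Φ((0.05 − 0.0744)/0.0384) = 26%

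| s | g (points) | Bias vs PCC / vs non-PCC (points) | Significant, 450 per arm | Significant, 225 per arm |
|---|---|---|---|---|
| any | 0 | 0 / 0 | 2.5% / 2.5% | 2.5% / 2.5% |
| 50% | 5 | +2.5 / −2.5 | 9.9% / 9.7% | 6.9% / 6.7% |
| 50% | 10 | +5.0 / −5.0 | 26% / 27% | 15.5% / 15.4% |
| 50% | 15 | +7.5 / −7.5 | 50% / 54% | 29% / 30% |
| 70% | 15 | +4.5 / −10.5 | 26% / 68% | 15% / 39% |
| 85% | 5 | +0.75 / −4.25 | 4.2% / 9.8% | 3.6% / 6.6% |
| 85% | 15 | +2.25 / −12.75 | 10% / 60% | 7.2% / 31% |

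The nominal rate in one direction is 2.5%.

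**3. Dividing both arms by intended agent.** Within the PCC-intended stratum both arms have expected rate 0.70 − (1 − s)g, and within the other stratum 0.70 + s·g. The expected difference is zero in each, whatever g is, and the two-sided rate stays at 5%.

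**4. Dose rows.** With an assumed high-dose share *h* = 20–50% and the same gaps, the bias is (1 − h)g in the high-dose row (0.50 × 5 = 2.5 to 0.80 × 15 = 12 points). It is h·g in the low-dose row (0.20 × 5 = 1 to 0.50 × 15 = 7.5 points), with the opposite sign.

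**5. Does another analysis already fill the gap?** Sensitivity analyses 1 and 5 (SAP 5.3.3) stratify by intended PCC use, and SAP 5.2.1 and 6.2.2.1 tabulate it. Each of those sensitivity analyses returns one overall estimate, so none gives a randomized effect by intended agent. For dose, 5.8 already has both-arm rows for prior inhibitor, for "Time to randomization since the last FXa inhibitor dose" and for two splits of baseline anti-fXa activity.

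**The case against.** Several points on the other side stand.

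- **The rows are only supportive.** SAP 5.1.1 confines confirmatory testing to the primary and secondary endpoints, and Protocol 10.8 says only that subgroup analyses may include these.
- **The row names disclose the contrast.** A careful reader can see that one arm is undivided. Table and figure layout is also out of view: "figure, and listing specifications are contained in the Data Presentation Plan in a separate document". A reader might infer that the plot will show these rows unmarked among the others. The documents do not settle that. What can be said is that 5.8 prescribes CMH inference and a forest plot with no exception for them.
- **Prognosis.** Protocol 3.2.1 offers regional difference in use as an alternative reason for the stratum. That is a precaution, not evidence that PCC recipients fare differently. A reader might infer a known bias in a known direction, but the documents give neither.
- **Size.** Every input that drives it is assumed. At 225 per arm the largest expected |z| on the grid is 0.114/√(0.21/225 + 0.814 × 0.186/54) = 1.86 (s = 0.76, g = 0.15), which is below 1.96.
- **Definition of non-PCC.** Elsewhere the SAP summarises "based on dose of andexanet received (low, high, and total) or the type of UC initially received (PCC, other, no treatment, and total"), so the plain complement is other agents plus no treatment. That is adequate if read literally.
- **Intended agent answers a different question** from andexanet versus PCC as given. This is so, and the remedy should say it.

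A reader might also infer that the dose rows are equally flawed, since the illustrated ceilings are close (12 against 12.75 points), and that usual-care patients should be classified by the regimen they would have received. The ceilings reflect the assumed inputs and do not rank the two problems. Dose rests mainly on pre-randomization facts, several of which already have both-arm rows. Protocol 3.3.2.2 does link baseline anti-fXa activity to hematoma expansion, but that activity is among those rows. A derived regimen variable would add little. It would also misplace some patients near the 8-hour boundary, because the dosing table counts time to andexanet start, which may be up to 30 minutes after randomization.

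What survives is that inference designed for randomized groups is specified for contrasts that are not randomized, with no caution in 5.8, while a randomized counterpart to the main one is already recorded in both arms.

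**Conclusion.** The point holds, as a minor one. The UC-received rows compare the andexanet arm with usual-care patients selected by an open-label choice made after randomization, and stratifying by onset-to-scan time does not correct for that. If prognosis differs by agent, the two rows are biased in opposite directions with no true effect. The size is zero with no gap. Under an assumed 50–85% PCC share and 5–15 point gap it is about 1 to 7.5 points versus PCC and 2.5 to 13 versus non-PCC, with signs that depend on an unknown direction. The dose rows are a lesser case.

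It would be wrong to conclude that the trial's main result is at risk. The primary test, the stopping rule and the alpha hierarchy use whole randomized arms and are unaffected. The harm is limited to misreading supportive rows. Confidence is high on what 5.8 specifies; whether any bias would occur is unknown.

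**What to change.** 1. Add intended usual-care agent, as recorded at randomization, to the 5.8 list as a both-arm subgroup. Use one label for it: Protocol 3.2.1 contrasts plasma-derived factor concentrates with other agents, whereas SAP 1.2 speaks of intended PCC use. State that the row estimates the effect by intended, not received, agent, and that participants without the record drop out.
2. Report the UC-received and dose contrasts as descriptive, labelled non-randomized, without CMH inference and apart from the randomized-subgroup forest plot. State whether dose means assigned or received. SAP 5.5.6 and 5.7.1 use dose received, and the per-protocol rules in SAP 6.1 foresee that the two can differ.

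The cost is a few lines of SAP text and minor programming. Protocol 10.8 already allows further subgroups. The new row loses participants with no intended-agent record, some of them enrolled before Amendment 1. Nothing in trial conduct or dosing changes.
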